Appendix 11 Telemedicine

OVERVIEW

All general study details at site(s) using telemedicine (TM) to enroll patients are identical to those sites not participating in TM. The Telemedicine Principal Investigator (TM PI) has the same study-related responsibilities as the Principal Investigators who are not participating in TM. The differences are primarily in the logistics of study assessments, methods of interactions with patients, and data collection through TM. These differences are outlined here.

RECRUITMENT

Patients will be recruited from selected site(s) within the United States where the TM investigators are licensed to practice medicine and provide tele dermatology clinical care.

INFORMATIONAL WEBSITES

Patients will be referred to an informational website about the pemphigus vulgaris (PV) study from various recruitment sources. Those who express interest will contact the TM PI or request to be contacted by the TM PI to discuss the details of the PV study and the specifics of the TM.

SCREENING PERIOD PROCEDURES

PRE-SCREENING

The TM research coordinator or TM PI will directly call the patient to confirm the basic eligibility criteria. If the patient meets all pre-screening eligibility criteria and is interested in participating, the following steps will occur:

- The electronic Informed Consent Form (eICF) will be made available for the patient to review, and the TM PI will schedule a follow-up call to review the eICF and any associated questions.
- The patient will be required to complete a medical information release form (compliant with the Health Insurance Portability and Accountability Act [HIPAA]) permitting the TM PI to contact the local dermatologist (LD) to discuss the patient, to obtain relevant medical records, and to verify eligibility criteria.

Informed Consent

- The TM PI will conduct the informed consent process with the patient. The TM PI/TM research coordinator will review the eICF with the patient and answer questions about the study. After the patient has had ample time to review the eICF, the TM PI or TM research coordinator will address any additional questions, the patient will sign the eICF, and the TM PI or TM research coordinator will countersign the eICF. After the informed consent form and eICF have been completed, the

Rituximab—F. Hoffmann-La Roche Ltd
130/Protocol WA29330, Version 5

Appendix 11 Telemedicine (cont.)

TM PI will continue to verify eligibility and proceed with the standard screening and enrollment procedures, as defined in the protocol.

Verification of Eligibility

- The TM PI will verify with the patient that he or she meets the inclusion and exclusion criteria specified in the protocol.
- The TM PI will contact the LD to obtain pathology reports and any other relevant medical information and supportive records to verify inclusion and exclusion criteria.

Transition of Care Responsibility

- After the eICF is completed, the TM investigators will assume responsibility of care for the patient regarding PV and associated medications (both study-related investigational medications and concomitant therapies for PV) and for all study-related decisions. The TM investigators will interact with the patient via TM, as is typical for this type of care in TM. The TM investigators will coordinate this transition of care with the LD and interact with the LD as needed throughout the study.

SCREENING (DAY – 28 TO DAY – 1)

Logistics and Planning for Study Visit at the Patient’s Home

A mobile research nurse (MRN) will visit patients at their home for the initial (screening) visit if they reside in states that allow the patient-physician relationship to be established through TM.

1. After the eICF is signed and all pre-screening criteria are met, an initial visit from the MRN will be scheduled at the patient’s home.
2. An iPhone® will be shipped pre-loaded with the necessary TM applications and software to the MRN.
3. The MRN will be trained on how to use the TM application, how to photograph patients reproducibly, and all relevant details of the study.
4. The MRN will bring the iPhone to the patient’s home for the screening visit. The iPhone will remain with the patient for the duration of the study.

Screening Visit in the Patient’s Home

1. A secure video conference will take place between the TM investigators, the patient, and the MRN at the patient’s home, using the iPhone. During this session, the following will occur:
 - Final details of inclusion and exclusion criteria will be re-confirmed.
 - The patient will be oriented to the functionality and usage of the iPhone and the TM application with assistance of the MRN.

Rituximab—F. Hoffmann-La Roche Ltd
131/Protocol WA29330, Version 5

Appendix 11 Telemedicine (cont.)

- Study logistics will be discussed, and any additional questions will be answered.
2. The MRN will conduct and record the following assessments:
- Body weight
 - Height
 - Vital signs
 - Collect all screening laboratory samples
 - Disease activity will be assessed:
 - The MRN will establish the best circumstances and location in the home for medical photography (i.e., lighting, privacy, etc.). The MRN will use the TM application to photograph all areas of the body and mucosa using standardized anatomic positions and transmit the images using a HIPAA-compliant platform in accordance with American Telemedicine Association Teledermatology guidelines. One entire set of images will be transmitted (these will be used to determine the Pemphigus Disease Area Index [PDAI]; see Day 1 assessment of disease activity below). The quality of photographs will be confirmed immediately by the efficacy assessor in the event that additional photographs need to be taken.
 - The efficacy assessor will evaluate the photographs sent by the MRN (see Step 1 above) to determine the screening PDAI.
 - Review all other requirements of the study with the patient using the TM application, including capture of the following information:
 - Any other new medical issues and other relevant medical history
 - Concomitant medications
 - Confirmation of the current prednisone dose and the safety assessor's instructions for the prednisone taper
 - Confirm that the patient is scheduled for a physical examination, electrocardiogram (ECG), and chest X-ray (CXR) with a local healthcare provider and radiology facility, respectively, to occur in a timely fashion. These reports will be reviewed by the safety assessor before any study treatments are initiated and administered.

Assessments

- Complete physical examination:

A complete physical examination will be conducted by the local healthcare provider. The findings will be reported to the safety assessor, who will review the findings and document appropriately.
- ECGs:

Rituximab—F. Hoffmann-La Roche Ltd
132/Protocol WA29330, Version 5

Appendix 11 Telemedicine (cont.)

ECGs will be conducted by the local healthcare provider. The findings will be reported to the safety assessor, who will review the findings and document appropriately.

- CXR:

The patient will go to a local radiology facility for a baseline CXR. The CXR report will be sent to the safety assessor, who will review the report and document appropriately.

Logistics and Planning for Study Visit at TM PI site

In states where the patient-physician relationship must be established in person before TM-based patient care is conducted, the initial (screening) visit will occur at the TM PI site.

After the eICF is signed and all pre-screening criteria are met, the TM research coordinator will schedule a day when the patient will travel to the TM site to complete the screening visit.

1. The screening visit assessments will be completed as outlined in the schedule of assessments ([Appendix 1](#)).
2. Study personnel will instruct the patient on the basic functions of the TM technology and iPhone use during the visit.
3. The patient will be sent home with an iPhone pre-loaded with TM technology for study use.

RANDOMIZATION (DAY 1, WEEK 1)

- After all of the screening procedures are confirmed and within 72 hours prior to the Day 1 infusion, the patient will be randomized using an interactive web/voice response system (IxRS), as detailed in Section 4.2.
- Once the patient is randomized, an unblinded TM research pharmacist will prepare study treatments as specified (rituximab, mycophenolate mofetil [MMF], matching placebos, methylprednisolone, and saline solution). Blinded study treatments will be dispensed to the MRN/infusion center staff. The pharmacy will also prepare non-study medications at the discretion of the TM investigator or per local guidelines (e.g., prednisone, gastrointestinal prophylaxis, *Pneumocystis jirovecii* pneumonia prophylaxis, topical agents) to be dispensed to the MRN/infusion center staff. For non-study medications, the patient may use their local pharmacy if desired.

Rituximab—F. Hoffmann-La Roche Ltd
133/Protocol WA29330, Version 5

Appendix 11 Telemedicine (cont.)

INFUSION DAYS 1 (WEEK 1), 15 (WEEK 2), 168 (WEEK 24), AND 182 (WEEK 26)

All patients, regardless of state of residence, will receive their infusions and associated study visit assessments at the TM PI site.

- Infusions: Rituximab (and matching placebo) should be administered in a hospital, clinic, or healthcare-related environment where full resuscitation facilities are immediately available and under the close supervision of an experienced healthcare professional.
- All infusion reactions and adverse events will be documented and communicated immediately, as appropriate, to the TM safety assessor and the Sponsor as per the protocol.
- Infusion day laboratory assessments:
 - All laboratory assessments scheduled for infusion days should be performed as described in the schedule of assessments (see [Appendix 1](#)). Blood draws that are timed to occur before and after the first infusions will be performed at the infusion center.

ALL OTHER STUDY VISITS

Weeks 4–20 and 32–52, Withdrawal, and Safety Follow-Up (Weeks 12, 24, 36, and 48 after Withdrawal or Completion of Treatment)

For all patients, regardless of state of residence, these study visits will be conducted by a MRN at the patient's home.

- TM research coordinator coordinates with MRN to schedule visits to the patient's home

Assessments specified for evaluation days other than infusion days should be performed within 3 days of the scheduled visit.

The MRN will visit the patient's home on each evaluation day noted in the schedule of assessments (see [Appendix 1](#) and [Appendix 2](#)). Assessments and procedures, including laboratory assessments and recording of adverse events and concomitant medications will be performed by the MRN. Results will be made available to the safety assessor via the TM application.

For assessments of disease activity:

- Disease activity will be assessed by the patient using the Patient Global Impression of Change (PGIC). The patient will complete the patient-reported outcome (PRO) questionnaires (Dermatology Life Quality Index [DLQI], European Quality of Life

Rituximab—F. Hoffmann-La Roche Ltd
134/Protocol WA29330, Version 5

Appendix 11 Telemedicine (cont.)

5-Dimension Questionnaire, three-level version [EQ-5D-3L], and Skindex-29), and the MRN will collect and mail the completed forms to the TM site.

- The MRN will use the TM application to photograph all areas of the body and mucosa; these photographs will be transmitted to the efficacy assessor for PDAI scoring and Clinician Global Impression of Change (CGIC) determination. The MRN will use the same location in the home as previously used to limit unnecessary variability.

DATA

All laboratory results will be transmitted securely to the safety assessor. As described in the protocol, the efficacy assessor will review all of the efficacy data and the safety assessor will review the laboratory data and all efficacy and safety data independently.

Within 24 hours, the efficacy assessor will evaluate disease activity, lesion count, flare assessment, calculate the PDAI score, and complete the CGIC. The safety assessor will make all treatment decisions. The safety assessor will call the patient to discuss all study treatment and management decisions. Serious adverse events, non-serious adverse events of special interest, and pregnancies will be reported to the Sponsor within 24 hours.

Safety data from TM will be reviewed by the independent Data Monitoring Committee (see Section [3.1.4](#)).

ANALYSES AND DECISION POINTS TO CONTINUE TM

Initially, approximately 10 patients will be recruited for participation in TM. Adverse events, data quality and completeness, and enrollment statistics will be reviewed monthly by the Sponsor and compared with the general enrollment arms of the study. The TM investigators will ensure that the images and data collected via TM provide adequate information for evaluating the primary efficacy endpoint and for ensuring patient safety.

Rituximab—F. Hoffmann-La Roche Ltd
135/Protocol WA29330, Version 5

Appendix 11 Telemedicine (cont.)

The measures of success of TM will include, *but is not limited to*, the screening and enrollment rates at the TM site(s), *iDMC review of the safety data, health authority interactions*, as well as the *Sponsor's review of the quality and completeness of the data*, in determining whether to continue or expand participation in TM. Analyses will be performed comparing the average performance with all other traditional (non-TM) sites, including, but not limited to:

- Total number of missed study days
- Average percentage of missing data per visit
- Screening rate
- Enrollment rate
- Retention rate (or dropout rate)

1. BACKGROUND

Study WA29330 (PEMPHIX) aims to evaluate the efficacy and safety of rituximab (RTX) versus mycophenolate mofetil (MMF) in patients with Pemphigus vulgaris (PV). PV is a rare, serious autoimmune disease characterized by blisters and erosions of the skin and mucosal areas.

Study WA29330 is a multicentre, randomized, double-blind, double-dummy, active-comparator, two-arm, parallel-group study, which consists of three periods: a screening period of up to 28 days, a 52-week, double-blinded, treatment period followed by a 48-week safety follow up (SFU) period, that begins at the time of study treatment completion or discontinuation.

This preliminary Statistical Analysis Plan (SAP) describes the statistical methodology and data handling rules to be used for the Week 52 primary analysis. The primary reporting event will include all data up to Week 52 or early withdrawal. The SAP will be finalized prior to database lock and data unblinding for the primary analysis.

A final reporting event and study database lock will occur after all patients complete the 48-week SFU period or withdraw early from SFU, details of which will be documented in a separate SAP.

2. STUDY DESIGN

2.1 PROTOCOL SYNOPSIS

The Protocol Synopsis is provided in [Appendix 1](#). Additional details including the study flowchart, schedule of assessments, and corticosteroid treatment guideline can be found in the Appendices ([Appendix 2](#), [Appendix 3](#), and [Appendix 4](#)).

2.2 OUTCOME MEASURES

2.2.1 Primary Efficacy Outcome Measures

The proportion of patients (excluding telemedicine [TM] patients) who achieve a sustained complete remission without experiencing an event that constitutes treatment failure (as defined in Section [4.2](#)) beforehand, during the 52-week treatment period.

Sustained complete remission is defined as achieving healing of lesions with no new active lesions (i.e., pemphigus disease area index [PDAI] activity score of 0) while on 0 mg/day prednisone or equivalent, and maintaining this response for a total of at least 16 consecutive weeks, during the 52-week treatment period. Patients with transient new lesions for 1 week or less that heal without additional systemic corticosteroid therapy will not be considered to have experienced treatment failure.

Rituximab—F. Hoffmann-La Roche Ltd
6/Statistical Analysis Plan WA29330

2.2.2 Secondary Efficacy Outcome Measures

The secondary efficacy outcome measures are as follows:

- Cumulative oral corticosteroid dose (prednisone or equivalent) over the treatment period
- Total number of disease flares during the treatment period
- Time to initial sustained complete remission
- Time to disease flare
 - Disease flare is defined as appearance of three or more new lesions a month that do not heal spontaneously within 1 week, or by the extension of established lesions, in a patient who has achieved disease control.
- Change in health-related quality of life (HRQoL), as measured by the dermatology life quality index (DLQI) score, from baseline to Week 52
- Duration of sustained complete remission
- Patients' impression of change in PV symptoms, as measured by the patient global impression of change (PGIC) score, during the treatment period
- Clinician impression of change in patients' PV symptoms, as measured by the clinician global impression of change (CGIC) score, during the treatment period.

The first five secondary efficacy outcome measures will be included in a hierarchical testing procedure to control for Type I error (See Section 4.7); the remaining secondary endpoints will be considered exploratory and will not be tested for Type 1 error.

2.2.3 Safety Outcome Measures

The safety outcome measures are as follows:

- Nature, frequency, and severity of adverse events (AEs), including serious adverse events and AEs leading to discontinuation
- Vital signs and clinical laboratory test results (including complete blood count and blood chemistry)
- Incidence of anti-drug antibodies(ADA)
- Circulating B cells, T cells, natural killer (NK) cells, plasma cells, and other leukocytes
- Plasma immunoglobulin (Ig) levels (total Ig, IgG, IgM, and IgA)
- Corticosteroid-related AEs in relation to corticosteroid exposure

2.2.4 Exploratory Outcome Measures

The exploratory outcome measures are as follows:

- Proportion of patients achieving a complete remission by Week 24 and by Week 52

Rituximab—F. Hoffmann-La Roche Ltd
7/Statistical Analysis Plan WA29330

Complete remission is defined as achieving wound healing with no new active lesions (i.e., PDAI activity score of 0) for at least 8 consecutive weeks during the 52-week treatment period.

- Proportion of patients achieving a partial remission by Week 24 and by Week 52
Partial remission is defined as the presence of transient new lesions that heal within 1 week (while the patient is receiving minimal therapy, including topical corticosteroids). Minimal therapy is defined as ≤ 10 mg/day prednisone (or equivalent) for at least 8 consecutive weeks during the 24-week or 52-week treatment period.
- Pharmacokinetics/pharmacodynamics (PK/PD) of RTX
PK/PD parameters include, but are not limited to, serum levels of RTX, peripheral CD19+B-cell counts, HACA, and autoantibody concentrations.
- To explore the PD of MMF in patients with PV
- Change in total PDAI activity score during the treatment period
- Change from baseline in anti-desmoglein-1 (Dsg1) and anti-desmoglein-3 (Dsg3) autoantibodies
- Change in health utilities as assessed by the European quality of life (EuroQoL) 5-dimension questionnaire, 3-level version (EQ-5D-3L) score from baseline to Week 52
- Change in HRQoL, as measured by the Skindex-29 from baseline to Week 52
- Proportion of patients experiencing treatment failure from Week 12 to Week 52.

2.3 DETERMINATION OF SAMPLE SIZE

The primary efficacy endpoint of this study is the proportion of patients (excluding TM patients) achieving a sustained complete remission, as assessed at Week 52, that has been maintained for ≥ 16 consecutive weeks during the 52-week treatment period. With use of limited data available in the literature from randomized clinical trials of MMF and investigator-initiated trials of rituximab ([Beissert et al. 2010](#)), it is estimated that approximately 40% of patients with PV receiving MMF will achieve a sustained complete remission. It is estimated that patients receiving rituximab will induce a sustained complete remission rate of 65%. On the basis of these assumptions, a total of 122 patients randomized to either the rituximab arm or the MMF arm in a 1:1 ratio (61 patients in the rituximab arm and 61 patients in the MMF arm) will yield approximately 80% power in a two-sided test at the 5% significance level. To account for the 10 TM patients excluded from the primary efficacy analysis, approximately 132 patients will be randomized in total. The sample size calculation was performed using nQuery Advisor 7 using the two-group chi-squared test of equal proportions. The primary analysis method using a Cochran-Mantel-Haenszel test adjusting for stratification factors is expected to provide at least 80% power to detect the difference in proportions.

Rituximab—F. Hoffmann-La Roche Ltd
8/Statistical Analysis Plan WA29330

No adjustment will be made for dropouts. Patients withdrawing early from the study or meeting the criteria for treatment failure (including rescue therapy) will be assessed based on available data up until the point of withdrawal or treatment failure only for the primary endpoint. Patients with missing or incomplete data where a status cannot be determined after applying relevant imputation rules will be set to non-responders.

2.4 ANALYSIS TIMING

The primary analysis will be conducted when all patients have completed the Week 52 study visit or have withdrawn early from the study. The reporting event for the primary analysis will include data for all patients up to their Week 52 assessment visit within the treatment period, or data up to the point of withdrawal. Safety follow up (SFU) data will not be included within the primary analysis data-cut. All data up to the Week 52 study visit will form part of the Primary Week 52 Clinical Study Report (CSR).

A final reporting event and study database lock will occur after all patients complete the 48-week SFU period or withdraw early from SFU, details of which will be documented in a separate SAP and final CSR. The final CSR will include all available data up to study completion (last patient's last visit [LPLV] in SFU) or early withdrawal from SFU.

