6. STATISTICAL CONSIDERATIONS AND ANALYSIS PLAN

Full details of all statistical methods and planned statistical analyses will be specified in the Statistical Analysis Plan (SAP), which will be finalized prior to locking and unblinding of the database. All efficacy outcomes will be analyzed according to the *modified intent-to-treat (mITT) population* and will include all randomized patients, *with exception of TM patients*, who have received any amount of study drug.

Treatment period data will be locked after all patients have completed the Week 52 visit. The primary efficacy (*excluding TM patients*) and safety analyses will be performed on data for patients through the Week 52 assessments or early discontinuation. A final database lock will occur after all patients have completed the trial, including the SFU period.

Safety assessments will be performed on patients who are evaluable for safety. In all safety analyses, patients will be grouped according to the treatment received rather than the treatment assigned.

Every effort will be made to obtain all scheduled efficacy and safety assessments for each patient. Patients who miss any scheduled doses or assessments will continue participation in the study and will continue to receive study drug.

Primary imputation methods for missing data will be specified in the SAP.

As part of a sensitivity analysis, *the inclusion of TM patients*, missing data patterns and associated missing data mechanisms will be further explored and analyzed as appropriate. The assumptions and methodology will be specified in SAP.

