4.5 DATA-CUT FOR ANALYSES

For each patient, the day of first dose of study treatment will be designated study day 1. Each subsequent assessment point will be assigned a study day calculated as:

date of assessment – date of first dose+1.

Data beyond the Week 52 visit will not be included in the primary Week 52 CSR. For each patient, data will be cut-off and reported up to and including the earliest of the following:

- Week 52 visit (using upper visit window of Day 364+10 days)
- Date of early withdrawal

Patients who complete the 52-week treatment period but have a missing Week 52 visit, or where the Week 52 visit falls outside the reporting cut-off will be evaluated up to study Day 365 for all analyses involving a duration or exposure element. In such analyses, any references to Week 52 throughout this SAP will imply study day 365 for these patients.

Although SFU data will not be included in data displays for the Week 52 primary reporting event, any deaths at the time of the data-cut, occurring in SFU will be highlighted in the CSR.

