4.9 SAFETY ANALYSES

The safety analysis will be performed on the safety population as defined in Section 4.1.3. Analyses of safety data up to Week 52 will include rescue patients up to the point of rescue only. Post-rescue data for patients who receive rescue therapy will be summarized separately for selected key safety outputs.

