4.9.2 Adverse Events

Adverse events will be mapped and reported using the Medical Dictionary for Regulatory Activities (MedDRA) thesaurus using the most current version at the time of analysis (version 17.1 or later). Glossaries showing the mapping of investigator verbatim terms to coded events will be produced.

A listing of AEs occurring during screening (prior to Day 1) will be produced to capture AEs occurring during the oral corticosteroid taper.

Treatment-emergent AEs (TEAEs) will be summarized. All AEs referenced in the section below will be TEAEs. TEAEs are defined as those AEs with observed or imputed onset date on or after the start date of trial treatment. Only where the most extreme intensity is greater than the initial intensity (or if most extreme intensity is not missing and initial intensity is missing) will events with an onset date prior to the start of trial treatment be considered treatment-emergent. An AE with a completely missing start date will be assumed to be treatment-emergent unless the AE has a complete non-imputed end date that is prior to study Day 1.

Listings will show all AEs reported, including AEs occurring after rescue therapy, and any AEs that may have occurred during the oral corticosteroid dose adjustments in the screening period.

AEs will be summarized by system organ class (SOC) and preferred term (PT), and will be presented in order of descending frequency summed across the treatment arms within each SOC and PT.

The following will be summarized, and/or listings produced where required:

- AEs
- Serious Adverse Events (SAEs)
- AEs by relationship to study medication
- AEs leading to study drug dose modification or interruption
- AEs by common terminology criteria grade
- Infections
- Serious Infections
- Corticosteroid-related AEs
- Infusion related reactions (IRRs) (Roche Standard AE Grouped Term [AEGT] MedDRA Basket)
- Serious IRRs
- AEs leading to withdrawal

Rituximab—F. Hoffmann-La Roche Ltd
31/Statistical Analysis Plan WA29330

- AEs leading to death
- Opportunistic infections (OI) , including serious OI (Roche Standard AE Grouped Term [AEGT] MedDRA Basket for Opportunistic Infections)

If an imbalance in exposure is found between treatment groups, AE rates per 100 patient-years exposure may be calculated. AE rate per 100 patient-years is defined as:

$$(\text{number of events} \div \text{total exposure}) \times 100$$

The 95% CIs will be calculated based on exact X^2 distribution.

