3.1 ANALYSIS POPULATIONS

The primary analysis populations are defined in the primary SAP, Section 4.1.

The rescue population (RP) includes patients who received at least one rescue therapy during the study (i.e., between Week 12 to Week 52 of the study treatment period).

The analysis populations in SFU will be the subset of patients in the primary analysis populations who entered the SFU period.

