3.2 DATA-CUT FOR ANALYSES

SFU period begins at the time of study treatment completion (for patients who complete the 52-week treatment period) or discontinuation.

For each patient, start of SFU period will be earliest of the following:

- Cut-off for Week 52+1 day (i.e., Day 375+1 day)
- Date of early treatment discontinuation+1 day

Each subsequent assessment point will be assigned a study day calculated as:

date of assessment – date of first dose + 1.

For patients who had their Week 52 visit after the Week 52 cut-off date (Day 365+10 days), the Week 52 data will be included in the analysis of the SFU period.

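### The by-arm tables of first-year SAEs and serious infections stop at early withdrawal and at rescue, no planned table counts all first-year events by arm, and the cut-off dates of the two reports conflict

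*SAP*

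**What the plan says.** **Week 52 report.** Primary SAP 2.4 says "Safety follow up (SFU) data will not be included within the primary analysis data-cut". Section 4.5 ends each patient's data at the earlier of the early withdrawal date and the "Week 52 visit (using upper visit window of Day 364+10 days"). The one exception is deaths: "Although SFU data will not be included in data displays for the Week 52 primary reporting event, any deaths at the time of the data-cut" that fall in SFU are to be pointed out in the CSR. Protocol Section 6 agrees: "safety analyses will be performed on data for patients through the Week 52 assessments or early discontinuation". Section 4.9 adds a second cut: "Analyses of safety data up to Week 52 will include rescue patients up to the point of rescue only". Post-rescue data get a separate summary for selected outputs. Within those limits, 4.9.2 lists SAEs, infections and serious infections, and 4.10.1 puts all displays by treatment group. If exposure is unbalanced, "AE rates per 100 patient-years exposure may be calculated".

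**Collection after withdrawal.** Under Protocol 3.1.1 and Appendix 1 (footnote a), treatment failure before Week 12 leads to a withdrawal visit and entry into SFU, as does stopping both study drugs early. Protocol 5.3.1 keeps SAEs and all infections reportable in SFU, which lasts 48 weeks.

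**SFU report.** SFU SAP 3.1: "The analysis populations in SFU will be the subset of patients in the primary analysis populations who entered the SFU period". Sections 3.6 and 3.6.1 tabulate events with onset from the start of SFU, in patients who entered it. Section 3.2 sets that start at the earlier of "Cut-off for Week 52+1 day (i.e., Day 375+1 day") and the day after early treatment discontinuation.

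**The concern.** Comparing safety with MMF is a stated objective, and Protocol 1.4.2 presents this as the single pivotal trial for a benefit-risk assessment. Leaving before Week 12 is driven by outcome, so the time covered by the Week 52 tables may differ between arms, and crude percentages would then describe unequal follow-up.

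Stopping study drug does not end rituximab exposure in any biological sense. Protocol 3.3.1 cites 6 to 9 months of B-cell depletion after a course in rheumatoid arthritis, and Protocol 5.1.1.3 warns of infection after treatment. A serious infection soon after early withdrawal is attributable time for the arm, yet it is missing from the first-year comparison.

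The SFU tables do not fill the gap, because they combine patients at different distances from dosing. If the two reports use different boundary dates, some events could also be counted in neither report or in both.

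**Working it through.** Neither document gives a figure for this point, so there is none to reproduce. The check is a trace of the rules, followed by a range for the size.

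**1. Where an event is counted**

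| Event | Week 52 by-arm tables | SFU tables |
|---|---|---|
| SAE at Week 10, on treatment | counted | no |
| SAE at Week 20, withdrew at Week 10 | not counted (a death would be highlighted) | counted if the patient entered SFU |
| SAE at Week 30, rescued at Week 20, still in the treatment period | not counted; separate post-rescue summary | no; rescue patients handled separately |
| SAE at Week 70, completer without rescue | no | counted, in the same table as the second row |

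No planned table joins the first three rows by arm.

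**2. What the SFU tables mix**

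- Withdrawal at Week 12: Weeks 12 to 60 (12 + 48). SFU entry is 84 − 15 = 69 days (9.9 weeks) after the last infusion.
- Completer: Weeks 52 to 100 (52 + 48). SFU entry is 364 − 182 = 182 days (26 weeks) after the last infusion.

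**3. The boundary**

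- *Cut at the actual visit* (primary SAP 2.4, and one reading of 4.5). The visit is due on Day 364 ± 3, so Days 361-367. SFU starts on Day 375 + 1 = 376. Days in neither report: 375 − 367 = 8 to 375 − 361 = 14.
- *Cut at a fixed day*. Section 4.5 gives 364 + 10 = Day 374. Table 1 in primary SAP 4.6 closes the Week 52 window at Day 375, and SFU SAP 3.2 describes the cut-off as 365 + 10 = Day 375. The conflict is one day.
- *Early withdrawals*. Primary SAP 4.5 stops at early withdrawal; SFU SAP 3.2 starts the day after treatment discontinuation. If discontinuation comes first, an onset between the two dates can appear in both reports.

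**4. Size**

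From the documents: 132/2 = 66 per arm, so 66 × 52 = 3432 patient-weeks. Assumed: 5-20% of an arm leave, at Week 12 or Week 4. Share outside = p(52 − w)/52.

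- Week 12: 3.3 × 40 = 132 (3.8%) to 13.2 × 40 = 528 (15.4%) patient-weeks.
- Week 4: 3.3 × 48 = 158 (4.6%) to 13.2 × 48 = 634 (18.5%) patient-weeks.
- Serious infections at an assumed 5-20 per 100 patient-years: 2.54 × 0.05 = 0.13 to 12.18 × 0.20 = 2.44 per arm.

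*Crude percentages*, 5% against 20% leaving at Week 12, constant yearly hazard r. Proportion seen = (1 − p)(1 − e^(−r)) + p(1 − e^(−12r/52)). Half-width = 1.96√(2q(1 − q)/66), with q = 1 − e^(−r).

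| r | Between-arm shift (points) | 95% CI half-width (points) |
|---|---|---|
| 0.05 | 0.56 | 7.3 |
| 0.10 | 1.09 | 10.0 |
| 0.20 | 2.04 | 13.1 |

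*Rates to withdrawal*, same split. Rate = [12/52·h1 + (1 − p)·40/52·h2] / [12/52 + (1 − p)·40/52].

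- h1 = h2 = 0.10: 10.0 per 100 patient-years in both arms, no shift.
- h1 = 0.20, h2 = 0.10: 12.40 against 12.73, a shift of 0.33.
- Hazard 0.10 doubling after withdrawal: 10.0 in both arms, while full first-year rates are 10.38 and 11.54. A difference of 1.15 is missed.
- Half-width for a rate difference: 1.96√(2 × 0.10/66) = 10.8 per 100 patient-years.

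*Wider range for one arm*: yearly SAE hazard 0.10-0.20, 10-20% leaving at Week 12, hazard 1 to 3 times as high afterwards. The Week 52 table would miss 0.7 to 7.1 points of that arm's first-year SAE risk. The top figure needs a 20% withdrawal share, the 0.20 hazard and a tripling together.

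**The case against.** The cut is pre-specified in the protocol and has a rationale. Early withdrawals move to standard-of-care treatment, and SFU SAP 3.6.1 foresees rituximab use in SFU, so keeping those events apart from the randomised comparison is defensible. From Week 12, treatment failure no longer forces withdrawal. Rates per patient-year are available if exposure proves unbalanced. All of this stands. However, such rates adjust for unequal time and bring back no excluded event, and an on-treatment table is no reason to omit a supplementary complete one.

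Four stronger readings are tempting, and the documents do not support them:

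- *That no by-arm comparison of first-year SAEs exists.* Primary SAP 4.9.2 and 4.10.1 plan one up to the cut, and for completers without rescue it covers essentially the whole year.
- *That the later events are lost.* They are tabulated and listed under the SFU SAP, listings flag rescue patients and those given rituximab in SFU, and the final CSR takes in all data.
- *That the study-day clock restarts at SFU entry.* SFU SAP 3.2 still counts study days from first dose. Only the visit windows in 3.3 run from SFU entry.
- *That a gap in days is proven.* Table 1 in primary SAP 4.6 and SFU SAP 3.2 both point to a fixed Day 375, which would leave a one-day slip in 4.5. Against that, primary SAP 2.4 refers to the visit, and SFU SAP 3.2 itself opens by starting SFU at treatment completion. The text is ambiguous, and one reading leaves a gap.

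**Conclusion.** The point holds as a minor one, with medium confidence. Planned by-arm tables of first-year SAEs and serious infections are truncated at withdrawal and at rescue. Later first-year events in early withdrawals appear only beside completers' second-year events. The boundary between the two reports is worded inconsistently.

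The size rests entirely on assumed withdrawal shares and hazards, since the documents give none. In most scenarios examined the effect is a fraction of the confidence interval half-width; even the extreme one-arm shortfall of 7.1 points is below the 13.1-point half-width at the same baseline hazard. Constant hazard is itself doubtful, because corticosteroids raise infection risk (Protocol 5.1.3) and are to be tapered to zero by Week 24.

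The direction is unknown. More early failure on MMF would lower MMF counts and make rituximab look worse; adverse-event withdrawals on rituximab would do the opposite. A reader might infer that the truncation flatters rituximab, but nothing in the documents shows this. No efficacy conclusion or main safety conclusion is shown to depend on it.

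**What to change.** The SFU SAP describes the primary CSR as already finalised, so both changes belong in the SFU SAP and the final CSR.

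**(a) One supplementary table**, added under SFU SAP 3.6.1: by arm, whole safety population, SAEs, serious infections and deaths with onset from first dose to Day 364 regardless of withdrawal or rescue, each patient counted once, with rates per observed patient-year. Beside it, show a version censored at rescue or at later rituximab or another immunosuppressant.

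**(b) One anchor date.** State the day on which Week 52 data end and start SFU the next day, for completers and for early withdrawals alike. Use the same event, withdrawal or treatment discontinuation, in both SAPs.

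The cost is SAP wording and one table in two versions, from data already collected. SFU lasts 48 weeks, so anyone leaving at Week 4 or later can be followed to Week 52 (4 + 48 = 52), and later pemphigus treatments and immunosuppressants are recorded in SFU.

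The limits should be stated with the table:

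- The uncensored version is confounded by later standard-of-care therapy. The censored version will largely repeat the existing table for patients who start such therapy at once.
- SFU visits are 12 weeks apart, against 2 to 8 weeks in the treatment period, so non-serious infections are best left out.
- There are no data after consent is withdrawn. If half of the early withdrawals also withdraw consent, about half of the excluded events can be recovered.
- First-year follow-up is incomplete for withdrawals before Week 4.
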